## **2.8 Anticipated Time of Completion**

We estimate the study will take approximately 6-12 months to complete. Participants will be recruited from each of the 4 participating FRIEND sites.

## **2.9 Regulatory Compliance**

The DCC is working with The Eunice Kennedy Shriver National Institute of Child Health and Human Development (NICHD), the three participating FRIEND institutions, and the single Institutional Review Board (Johns Hopkins University) to ensure that clinical study data and regulatory requirements are met regarding the Food and Drug Administration (FDA) code for federal regulations. This trial is registered on <http://www.clinicaltrials.gov> (NCT04177693).

### 3 Background and Significance

#### 3.1 Overview

Uterine leiomyomas (fibroids) affect 30-50% of reproductive-age women and are a significant cause of infertility. Intramural and submucosal fibroids reduce the likelihood of pregnancy (RR=0.3-0.7) compared to unaffected women. Surgical removal of fibroids can restore fertility; however, recurrence rates are high, and benefits are often temporary. Importantly, serious postoperative consequences such as adhesions can adversely affect a woman's fertility and health in general. Hormonal therapies that induce medical menopause can be used to reduce fibroid size, but these therapies also prevent pregnancy. There is a critical need for effective, non-hormonal, non-surgical fertility treatment options for women with fibroids that may distort the uterine cavity. Our long-term goal is to develop novel non-hormonal treatments for uterine fibroids. Green Tea leaves contain polyphenols and catechins, such as epigallocatechin gallate (EGCG). Studies from our group and others have shown that EGCG is the most abundant and active compound responsible for effects of Green Tea extracts. Notably, EGCG can be taken during pregnancy and there are no known teratogenic effects. EGCG polyphenols inhibit key pathways of tumor growth by modulating signaling pathways involved in cell proliferation, transformation, inflammation, apoptosis, metastasis and invasion. Prior to initiating a randomized, double-blind, multi-center, prospective, clinical trial of EGCG versus placebo in women with uterine fibroids to evaluate birth rate a pharmacokinetic and hepatic safety analysis must be conducted. The pharmacokinetics and hepatic safety of EGCG with clomiphene citrate and letrozole are unknown. A 3-arm study will be conducted in women with and without fibroids to allow comparisons between these groups. The results of this study will be used to confirm hepatic safety for the larger multi-center FRIEND study.

#### 3.2 EGCG (Green Tea extract) and Uterine fibroids

[figure not shown]
Green Tea leaves contain polyphenols such as catechins or flavin-3-ols that include epicatechin (EC), epigallocatechin (EGC), epigallocatechin gallate (EGCG), and alkaloids. Catechins are the major components of tea phenols and constitute about 30-42% of the dry weight of Green Tea. Studies have shown that the EGCG catechin is the most abundant and active compound responsible for most of Green Tea's role in promoting good health and accounts for the favorable research result cited in the medical literature with the use of Green Tea extracts. EGCG have the highest level of polyphenols and makes it the major anti-oxidant agent in Green Tea. A study conducted by the United States Department of Agriculture reported that Green Tea has potent anti-neoplastic effects against a wide range of human tumor cells (4) EGCG polyphenol have been shown to inhibit key pathways of tumor growth. EGCG appears to block each stage of tumorigenesis by modulating signaling pathways involved in cell proliferation, transformation, inflammation, apoptosis, oxidative stress and invasion (4). Studies by [name] et al demonstrated increasing levels of Catechol-O-methyl transferase (COMT) in uterine leiomyoma compared to adjacent myometrium and described its important role in fibroid pathogenesis (5) Beside various useful antioxidant and anti-inflammatory effects, EGCG exerts a potent COMT inhibitor effect which also contribute to effective anti-fibroid action (2, 5). Additionally, published work by [name] also demonstrated the utility of EGCG for inhibiting fibroid tumor formation in vivo in nude mouse model (3). [name] research team (a member of this consortium) has reported that EGCG acting as anti-uterine fibroid agent through the modulation of multiple signal

transduction pathways. The group demonstrated that EGCG works on the gene level, to inhibit the proliferation of Human fibroid cells and induces apoptosis (2). This study also showed an impressive 14-fold increase in the expression of the BMP2 gene in EGCG-treated human fibroid cells than in the untreated control (2). That major increase in the secretion of BMP2 from fibroids by EGCG treatment is likely be able to overcome the fibroid-induced endometrial BMP-resistance through increased binding to the BMP receptors which will lead to improvement in the decidualization of the endometrium and subsequently enhancement of implantation, fertility and pregnancy outcomes. Furthermore, studies also demonstrated that EGCG significantly decreased TGF- $\beta$ 3 production by human fibroid cells. As TGF- $\beta$ 3 is the main cytokine responsible for endometrial BMP-resistance, such effect of EGCG would be expected to lead to improved endometrial receptivity.

### **3.3 EGCG Clinical trial in women with symptomatic uterine fibroids**

To translate the positive EGCG anti-fibroid preclinical findings in human fibroid cell lines and fibroid animal models, the efficacy and safety of EGCG on uterine fibroids burden and quality of life in women with symptomatic uterine fibroids were evaluated in an NIH-funded double-blinded, placebo-controlled randomized clinical trial(NCT 01311869) (1). A total of 39 reproductive-age women (age 18–50 years, day 3 serum follicle-stimulating hormone <12 IU/L) with symptomatic uterine fibroids were recruited for this study. All subjects had at least one fibroid lesion 2 cm^3 or larger in volume, as confirmed by transvaginal or transabdominal ultrasonography. The subjects were randomized to oral daily treatment with either 800 mg of decaffeinated EGCG or placebo (800 mg of brown rice) for 4 months, and uterine fibroid volumes were measured at the end of study, also by transvaginal or transabdominal ultrasonography. The fibroid-specific symptom severity and HRQL of these uterine fibroid patients were scored at each monthly visit, using the symptom severity and quality-of-life questionnaires (1). Of the final 39 women recruited for the study, 33 completed all five visits of the study. In the placebo group (n = 11), fibroid volume increased (24.3%) over the study period; however, patients randomized to green tea extract treatment (n = 22) showed significant reduction (32.6%, P = 0.0001) in total uterine fibroids volume. In addition, EGCG treatment significantly reduced fibroid-specific symptom severity (32.4%, P = 0.0001) and induced significant improvement in HRQL (18.53%, P = 0.01) compared to the placebo group. Anemia also significantly improved by 0.7 g/dL (P = 0.02) in the EGCG treatment group, while average blood loss significantly decreased (P = 0.001). No adverse effects, endometrial hyperplasia, or other endometrial pathology were observed in either group (1).

**Figure 1. Flowchart**

## 4 Objectives

### 4.1 Primary Aim

Our goal is to assess the pharmacokinetics and hepatic safety of EGCG in women with and without uterine fibroids.

### 4.2 Secondary Aim

Not applicable.

### 4.3 Treatment Design, Study Population, and Study Summary

#### 4.3.1 Treatment Design

This will be a pharmacokinetic trial involving 36 healthy adult female subjects. There will be 18 subjects with uterine fibroids and 18 without uterine fibroids. The randomization scheme will be coordinated through the DCC and the randomization will be stratified for age groups 18-29 and 30-40 and presence of fibroids. The population will consist of 36 women with or without uterine fibroids, age  $\geq 18$  to  $\leq 40$  years (at time of consent).

The appropriate study candidates will be recruited from the clinics of the 4 FRIEND Collaborative sites after obtaining informed written consent from the female subjects. Recruited participants will meet the inclusion and exclusion criteria detailed below. Monitoring of this trial at all sites will be conducted by the Yale DCC.

[figure not shown]
#### 4.3.2 Study Population

Thirty-six (36) patients will be equally randomized via computer-generated randomization schedule to receive:

1. Two capsules of decaffeinated Green Tea extract (close to 800mg EGCG) taken orally on a daily basis for up to 2 months
2. Two capsules of decaffeinated Green Tea extract taken orally on a daily basis for up to 2 months with clomiphene citrate 100mg for 5 days
3. Two capsules of decaffeinated Green Tea extract taken orally on a daily basis for up to 2 months with letrozole 5mg for 5 days.

#### 4.3.3 Study Summary

Recruitment and Prescreening: see Section 5 descriptions following.

Screening visit (anytime in cycle 1):

1. Obtain informed, signed consent.
2. Complete medical/gynecological/menstrual history and physical exam of female study participant.
  - Vital signs, height, weight, hip and abdominal circumference, BMI
  - Pap smear if necessary per current ACOG time-frame guidelines
  - Standard pelvic and breast exam conducted by physician or within past 12 months
3. Perform radiological exams.
  - Pelvic ultrasound measuring uterine and ovarian characteristics or within past 3 months
4. Laboratory tests: EGCG and metabolites, liver function, folate, estrogen levels, genetics sample collection and urine pregnancy test.
5. Dispense Green Tea extract and educate on dietary restrictions while taking Green Tea extract and with the importance of taking food. All patients to start Green Tea extract at this visit.
6. Contraception education. Patients will be counseled to use non-hormonal double-barrier method: a male/female condom plus spermicidal agents, cervical cap, diaphragm or sponge.
7. Concomitant medication collection.

Visit 1 (Day 1-5):

Patient will be seen on menstrual cycle day  $3 \pm 2$  days for clomiphene citrate/letrozole initiation visit

1. Vital signs and weight.
2. Laboratory tests: EGCG levels over 8 hours (0.5,1,2,4,6,8), liver function, folate, estrogen level, and urine pregnancy testing.
3. Concomitant medication collection and pill counts of EGCG.
4. Randomization and dispensation of clomiphene citrate/letrozole.
5. Contraception education. Patients will be counseled to use non-hormonal double-barrier method: a male/female condom plus spermicidal agents, cervical cap, diaphragm or sponge.

Visit 2 (day 8-10):

Patient will return several days after final clomiphene citrate/letrozole administration

1. Vital signs and weight.
2. Laboratory tests: EGCG levels over 8 hours (0.5,1,2,4,6,8), liver function, folate, estrogen level and urine pregnancy testing.

3. Concomitant medication collection and pill counts of EGCG and clomiphene citrate or letrozole as appropriate.
4. Contraception education. Patients will be counseled to use non-hormonal double-barrier method: a male/female condom plus spermicidal agents, cervical cap, diaphragm or sponge.

Visit 3 (day 14-16):

1. Pelvic ultrasound via a transvaginal probe or transabdominal transducer evaluation of endometrial thickness and ovarian characteristics.

Visit 4 (day 30-35):

Patient will return for final study visit.

1. Vital signs and weight, hip and abdominal circumference, BMI
2. Laboratory tests: EGCG and metabolites, liver function, estrogen level, folate, and urine pregnancy test.
3. Concomitant medication collection. Return unused medications and pill counts of EGCG.

Future Studies: One tube of blood will be collected at each visit to be stored for future analyses related to this study.

*4.3.4 Inclusion Criteria*

1. Healthy women  $\geq 18$  to  $\leq 40$  years of age with or without uterine fibroids
2. Must use a double-barrier method for contraception

*4.3.5 Exclusion Criteria*

1. Subjects using Green Tea/EGCG within 2 weeks prior to study enrollment. Matcha (Japanese green tea), maca powder, green tea beverages and all other forms of green tea require a 2-week wash-out. Patients with a detectable EGCG level at the screening visit will be excluded.
2. Known liver disease (defined as AST or ALT  $>2$  times normal, or total bilirubin  $>2.5$  mg/dL).
3. History of alcohol abuse (defined as  $>14$  drinks/week) or binge drinking of  $\geq 6$  drinks at one time).
4. Subject using hormonal contraceptives: 3-month wash-out is required for all oral or cyclic progestins, GnRH agonists/ antagonists, gonadotropins, injectable contraceptives, oral contraceptives, contraceptive implants and previous use of clomiphene and letrozole.
5. Subjects who are pregnant or breastfeeding
6. Known hypersensitivity to the study drugs
7. Any chronic disease

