### 2.4 Treatment

The 36 women will be randomized to one of the following groups:

1. EGCG daily alone.
2. EGCG daily with clomiphene citrate 100mg for 5 days.
3. EGCG daily with letrozole 5mg for 5 days.

The purpose of studying EGCG in combination with clomiphene citrate or letrozole is to assess the safety of using them together prior to the initiation of the FRIEND study. It is expected that EGCG will decrease fibroid size and decrease humoral activity leading to improved quality of endometrium for implantation. Clomiphene citrate and letrozole are being used for ovulation stimulation as treatment for unexplained infertility. In view of the possibility of interaction and change in toxicity when both are used together for FRIEND study, it was suggested by our pharmacology reviewer to include EGCG with the addition of clomiphene citrate and letrozole for the safety study.

The initial screening visit will include EGCG levels, liver function, folate and estrogen levels. A genetics sample collection, urine pregnancy test and pelvic ultrasound will also be performed after informed consent. Patient will be given the EGCG (Green Tea extract) to start after the screening visit. Patients will be counseled on dietary restrictions while on EGCG.

Visit 1 will occur on menstrual cycle day  $3 \pm 2$  days. EGCG levels over 8 hours, liver function, and urine pregnancy testing will occur at this visit. Patients will be assigned into their groups and provided with their respective treatments at this visit.

Patient will return between days 8-10 of the cycle for Visit 2. EGCG levels over 8 hours, liver function, estrogen, and urine pregnancy testing will occur at this visit.

The patient will return for Visit 3 between days 14-16 for a pelvic ultrasound evaluation of endometrial thickness and ovarian characteristics.

The final study visit (Visit 4) will be approximately 4 weeks after initiation of the study treatment and will involve EGCG levels, liver function, folate, and urine pregnancy test and pill counts.

The 4 lab panels (screening, Visits 1, 2, and 4) will include EGCG and metabolite analyses, liver panel (AST, ALT, total bilirubin, ALP) and estrogen levels, and a urine pregnancy test. The EGCG analyses at visits 1 and 2 will include testing over 8 hours.

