## 5.5 Randomization/Treatment Initiation

Thirty-six (36) patients will be equally randomized via computer-generated randomization schedule to receive: 1) 800 mg of decaffeinated EGCG taken orally on a daily basis with food for up to 2 months; 2) 800 mg of decaffeinated EGCG taken orally on a daily basis with food for up to 2 months with clomiphene citrate 100mg for 5 days; 3) 800 mg of decaffeinated EGCG taken orally on a daily basis with food for up to 2 months with letrozole 5mg for 5 days.

Treatment assignments will be randomized for age groups and presence of fibroids by a varying-block-size design. The DCC statisticians will generate the randomization scheme for the study.

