### 6.2 Primary Outcome Measurements

The primary outcome parameter will be differences in pharmacokinetic parameters of EGCG and 2 of the major metabolites between the 3 treatment groups.

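### EGCG sampling at Visits 1 and 2 has no pre-dose draw and stops at 8 h on daily dosing, so trough is unobserved and 24-hour exposure rests on an unplanned extrapolation

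*Combined protocol and SAP*

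**What the plan says.** **Profiles.** Section 4.3.3 gives the Visit 1 laboratory list as "EGCG levels over 8 hours (0.5,1,2,4,6,8), liver function, folate, estrogen level, and urine pregnancy testing", and Visit 2 has the same six EGCG times: "EGCG levels over 8 hours (0.5,1,2,4,6,8". The synopsis (section 2.4) agrees: "The EGCG analyses at visits 1 and 2 will include testing over 8 hours". Neither place lists a time-zero, 12 h or 24 h sample, and neither ties the times to an intake taken at the clinic.

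**Dosing.** EGCG begins at screening ("All patients to start Green Tea extract at this visit") and section 5.5 describes "800 mg of decaffeinated EGCG taken orally on a daily basis with food for up to 2 months". Both profiles are therefore repeat-dose profiles, and the concentration just before that day's intake need not be zero.

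**Other EGCG samples.** The screening sample precedes treatment, and section 4.3.5 adds: "Patients with a detectable EGCG level at the screening visit will be excluded". Visit 4 lists "Laboratory tests: EGCG and metabolites, liver function, estrogen level, folate, and urine pregnancy test", with no time since the last intake. Neither is a defined trough.

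**Outcome.** Section 6.2 states: "The primary outcome parameter will be differences in pharmacokinetic parameters of EGCG and 2 of the major metabolites between the 3 treatment groups". The parameters are not named there or in sections 2.5, 2.7 and 6.4. No extrapolation rule is given.

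**The concern.** The two combination arms exist because clomiphene or letrozole might interact with EGCG, and the results are meant to confirm hepatic safety for the larger trial. If either drug slowed EGCG elimination, much of the added exposure would fall after 8 h, where nothing is measured. Visit 2, after the five-day course, is the profile that could show it. Because the outcome names no parameter, nothing stops AUC0-8 from becoming the measure compared between arms. It would then shrink such an effect towards no difference, which is the wrong direction of error for a safety study. Trough is the most direct sign of accumulation on daily dosing, and it is not observed at all.

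**Working it through.** The plan states no figure for AUC, trough or half-life, so there is none to reproduce.

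**Inputs from the protocol:** samples at 0.5, 1, 2, 4, 6 and 8 h (section 4.3.3); daily intake (section 5.5); 36 women, two profiles each.

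**Assumptions, not in the documents:** one intake per 24 h; sampling times counted from that intake; one compartment with first-order absorption at steady state; half-life 2 to 12 h; absorption rate ka 0.5 to 2 per hour; 20% proportional error in the noise check.

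**Step 1. Hours unsampled.** 24 − 8 = 16 h.

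**Step 2. Model.** With k = ln 2 / half-life and a scale factor A (dose × bioavailability / volume):

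- C(t) = A·ka/(ka−k) · [e^(−kt)/(1−e^(−24k)) − e^(−ka·t)/(1−e^(−24ka))]
- AUC0-24 = A/k
- AUC0-8 = A·ka/(ka−k) · [(1−e^(−8k))/(k(1−e^(−24k))) − (1−e^(−8ka))/(ka(1−e^(−24ka)))]

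**Step 3. Worked case: ka 1, half-life 4 h, A = 1.**

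- k = 0.1733. AUC0-24 = 1/0.1733 = 5.77. AUC0-8 = 1.2096 × (4.397 − 1.000) = 4.11. Share observed: 4.11/5.77 = 0.71.
- Halve clearance, so k = 0.0866. AUC0-24 = 11.54. AUC0-8 = 1.0949 × (6.595 − 1.000) = 6.13.
- True ratio: 11.54/5.77 = 2.00. AUC0-8 ratio: 6.13/4.11 = 1.49.

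**Step 4. Range.** Each cell gives the share of AUC0-24 inside 0-8 h, then the AUC0-8 ratio when the true ratio is 2.00.

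| Half-life before interaction | ka 0.5 | ka 1 | ka 2 |
|---|---|---|---|
| 2 h | 84%; 1.54 | 90%; 1.57 | 93%; 1.60 |
| 4 h | 65%; 1.50 | 71%; 1.49 | 74%; 1.49 |
| 8 h | 49%; 1.66 | 53%; 1.61 | 55%; 1.60 |
| 12 h | 43%; 1.76 | 46%; 1.71 | 48%; 1.69 |

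With 3 h and 6 h included, the ratio runs from 1.49 to 1.76. A 25% fall in clearance (true ratio 1.33) appears as 1.18 to 1.25.

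**Step 5. Is the missing time-zero value the cause?** Setting it to zero changes AUC0-8 by at most 1.1% (ka 1). It is not; the shrinkage comes from truncation at 8 h.

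**Step 6. Can the tail be extrapolated?** Without noise, a log-linear slope through 4, 6 and 8 h recovers AUC0-24 within about 1.5% and a ratio of 2.00 to 2.02 (ka 1). With 20% error, the 5th to 95th percentiles of estimated/true values in one woman (ka 1) are:

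| Half-life | AUC0-24, 4-8 h slope | AUC0-24, with pre-dose value | Trough, 4-8 h slope |
|---|---|---|---|
| 2 h | 0.88-1.19 | 0.87-1.17 | 0.16-11.3 |
| 4 h | 0.84-1.44 | 0.87-1.16 | 0.14-8.4 |
| 8 h | 0.72-1.47 | 0.87-1.17 | 0.13-3.8 |

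At 8 h about 12% of profiles give no usable slope; the slope columns leave those out. The third column uses the pre-dose value as both the 0 h and the 24 h concentration, with a log trapezoid from 8 to 24 h.

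**Step 7. The integration rule matters.** A linear trapezoid from 8 to 24 h gives ratios of 1.85 to 2.00 and overstates AUC0-24 by 7 to 17% at half-lives of 2 to 8 h. The log trapezoid gives about 2.0.

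**The case against.** A reader might infer three stronger things, and the documents support none of them.

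- **That 24-hour exposure cannot be estimated.** It can. Three samples from 4 to 8 h give a terminal slope, and Step 6 shows that it does well at a short half-life. What is lost outright is an observed trough.
- **That an interaction will be understated.** This needs AUC0-8 to be the parameter analysed and half-life to be prolonged. The plan commits to neither. The same six samples also allow Cmax, half-life and an extrapolated AUC. If the interaction changes absorption or first-pass loss with half-life unchanged, the AUC0-8 and AUC0-24 ratios are equal. The protocol says only that the pharmacokinetics of the combinations are unknown.
- **That the absent pre-dose sample creates the bias.** Step 5 shows otherwise. The sample helps because, at steady state, it stands in for the 24 h value.

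The remedy also has limits, and these objections stand. Using the pre-dose value at 24 h assumes steady state and a known previous intake time. Visit 2 falls several days after the last clomiphene or letrozole dose, so any effect on EGCG may be fading. No section says that the existing blood is drawn before that day's intake, so the change involves more than a tube. Finally, the analysis is mainly descriptive and the plan calls itself underpowered, which lowers the stakes for formal testing. It does not help a descriptive summary that is itself shrunk towards no difference.

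**Conclusion.** The concern holds in a limited form. It is certain from the documents that trough is unobserved on both profile days and that no method is stated for the 16 unsampled hours. AUC0-24 is recoverable by extrapolation, adequately at a half-life of about 2 h and imprecisely from about 4 h upwards.

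The understatement is conditional. If AUC0-8 is compared and clearance is halved with half-life doubled, a true ratio of 2.0 appears as about 1.5 to 1.8 throughout the assumed range. The sizes rest on an assumed model, half-life, absorption rate and error; the direction did not change anywhere in that range. This is a gap worth closing because it touches the primary outcome and costs little. It does not invalidate the design.

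**What to change.** 1. **Sampling (sections 2.4, 4.3.3 and 5.9).** Add a 0 h EGCG and metabolite tube to the Visit 1 and Visit 2 profiles, drawn before that day's EGCG intake. State that the other times are hours after that intake.
2. **Records.** Capture the clock times of the previous and current intake.
3. **Parameters (sections 6.2 and 6.4).** Name trough, AUC0-8 and AUC0-24. Compute the 8 to 24 h segment by log trapezoid, with the pre-dose value as the 24 h concentration, and state the steady-state assumption.
4. **Sensitivity analysis.** Repeat AUC0-24 with log-linear extrapolation from 4 to 8 h, because steady state may not hold at Visit 2.
5. **Undetectable pre-dose values.** State a rule, since the log trapezoid needs a positive value; at a 2 h half-life the model (ka 1) puts trough at 0.07% of the peak. The 4 to 8 h extrapolation can serve for those profiles.

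**Cost:** one tube on each of two days that already have six timed draws; up to 36 × 2 = 72 extra assays; documentation of intake times. No visit is added and the treatment regimen is untouched.

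### The Visit 1 and Visit 2 cycle-day windows cannot always be met together with a Visit 2 several days after the last clomiphene or letrozole dose

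*Combined protocol and SAP*

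**What the plan says.** Section 4.3.3 (Study Summary) places Visit 1 on cycle day 3 ± 2, that is day 1 to 5, and describes it with the words "days for clomiphene citrate/letrozole initiation visit". Section 2.4 (Treatment) says of the same visit: "Patients will be assigned into their groups and provided with their respective treatments at this visit". Section 4.3.2 gives the length of the course in the two combination arms: "with clomiphene citrate 100mg for 5 days" and "with letrozole 5mg for 5 days".

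Visit 2 is placed in two ways. Section 2.4 counts it by cycle day: "Patient will return between days 8-10 of the cycle for Visit 2". Section 4.3.3 uses the same days in its Visit 2 heading, and then adds directly beneath: "Patient will return several days after final clomiphene citrate/letrozole administration". No number of days is attached to that interval, and nothing says which condition governs if they conflict.

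On sampling, section 2.4 states: "The EGCG analyses at visits 1 and 2 will include testing over 8 hours". The Visit 4 list in section 4.3.3 has EGCG and metabolites without 8-hour sampling. Section 6.2 defines the endpoint: "The primary outcome parameter will be differences in pharmacokinetic parameters of EGCG and 2 of the major metabolites between the 3 treatment groups".

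**The concern.** The first visit may fall on any of five cycle days, the course that starts there has a fixed length, and the second visit is fixed by cycle day rather than by the course. The interval from last dose to Visit 2 therefore moves with the day of Visit 1. For a late Visit 1, it shrinks to a point where the sentence about returning some days after the last dose cannot be honoured.

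This bears on the primary outcome. The second drug is first dispensed at Visit 1, so the Visit 1 profile cannot follow the course, and Visit 4 has no full profile. Visit 2 is the only 8-hour EGCG profile that can show the effect of a completed or nearly completed course. Section 2.4 gives possible interaction and altered toxicity as the reason for including the combination arms. If some Visit 2 profiles in an arm are taken during co-administration and others days after it, the arm summary does not describe one stated condition. The liver function and estrogen samples at Visit 2 have the same timing.

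The visit lists in section 4.3.3 call for a count of clomiphene or letrozole pills at Visit 2, but do not mention the date or time of the last dose. Unless the case report form captures it, the interval may not be recoverable afterwards.

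**Working it through.** The plan gives no figure for this interval, so there is nothing to reproduce. The check lists every permitted pair of visit days.

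**Inputs**

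- Visit 1 day, *v1*: 1 to 5 (section 4.3.3).
- Course length: 5 days (sections 2.4 and 4.3.2), so the last dose is 4 days after the first.
- Visit 2 day, *v2*: 8, 9 or 10 (sections 2.4 and 4.3.3).
- Start offset, *s*: 0 if the first dose is taken on the Visit 1 day, 1 if it is taken the next day. The documents call Visit 1 the initiation visit but do not state the day of the first dose. I take *s* = 0 as the main assumption and *s* = 1 as the sensitivity case.

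**Formulas**

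- Last-dose day = *v1* + *s* + 4
- Gap = *v2* − (*v1* + *s* + 4)

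**Results, in days**

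| Visit 1 day | Last dose, *s* = 0 | Gap at Visit 2 day 8 / 9 / 10 | Last dose, *s* = 1 | Gap at Visit 2 day 8 / 9 / 10 |
|---|---|---|---|---|
| 1 | 5 | 3 / 4 / 5 | 6 | 2 / 3 / 4 |
| 2 | 6 | 2 / 3 / 4 | 7 | 1 / 2 / 3 |
| 3 | 7 | 1 / 2 / 3 | 8 | 0 / 1 / 2 |
| 4 | 8 | 0 / 1 / 2 | 9 | −1 / 0 / 1 |
| 5 | 9 | −1 / 0 / 1 | 10 | −2 / −1 / 0 |

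**Same-day start.** The extremes are 8 − (5 + 0 + 4) = −1 and 10 − (1 + 0 + 4) = +5. Of the 5 × 3 = 15 pairs, 1 puts Visit 2 before the last-dose day and 2 put it on that day, so 3 of 15 are on or before it. With Visit 1 on day 5 the largest possible gap is 10 − 9 = 1 day. With Visit 1 on day 4 it is 10 − 8 = 2 days.

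**Next-day start.** The extremes are 8 − (5 + 1 + 4) = −2 and 10 − (1 + 1 + 4) = +4. On or before the last-dose day: 1 + 2 + 3 = 6 of 15 pairs.

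**Where the statements agree.** The plan does not define *several*. If it is read as 3 days or more, a same-day start satisfies everything for Visit 1 on day 1 (any Visit 2 day), on day 2 (Visit 2 on day 9 or 10) and on day 3 (Visit 2 on day 10). That is 3 + 2 + 1 = 6 of 15 pairs. With Visit 1 on day 4 or 5, no permitted Visit 2 day does so. A gap of at most 1 day fails any ordinary meaning of the word, so the conflict at day 5 does not depend on the cut-off.

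**The case against.** The strongest reply is that section 4.3.3 already ties Visit 2 to the last dose. The sentence stands directly under the Visit 2 heading, so the day window and the interval can be read as joint conditions. A site that followed both would not book a visit on or before the last-dose day. This stands in part. A reader might infer that Visit 2 has no stated relation to the last dose, or that the two conditions never fit together, and neither is true: early Visit 1 days can satisfy both. But for a permitted Visit 1 on day 5 there is no Visit 2 day that meets both conditions. The site must break one of them, and the protocol does not say which.

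Second, the counts are not forecasts. A reader might turn 3 of 15 into a statement that 20% of women will be profiled while still on drug. The documents give no distribution of visit days, so the fractions describe the calendar only. Such profiles can occur; nothing shows that they will.

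Third, the harm is not quantified. It is tempting to say that the arms will mix exposed and washed-out women and that any interaction will be diluted. That would need the elimination of clomiphene and letrozole and the duration of any effect on EGCG, and the documents give neither. This objection stands in full.

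Fourth, the plan does not name Visit 2 as the primary timepoint. Sections 2.7 and 6.4 also call the analysis descriptive and expect too little power for formal inference, although they plan a two-way ANOVA on treatment and fibroid status. This tempers the point. Even so, the sampling schedule leaves Visit 2 as the only full profile that can follow the course, and a descriptive summary also needs a defined interval.

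**Conclusion.** The point holds as an internal inconsistency at the late end of the Visit 1 window. With a same-day first dose, the gap from last dose to Visit 2 can run from −1 to +5 days. It is at most 1 day for Visit 1 on day 5 and at most 2 days for day 4, and 3 of the 15 permitted pairs fall on or before the last-dose day. With a next-day first dose, the range is −2 to +4 days and the count is 6 of 15. The conflict remains under either assumption about the first dose.

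The consequence is one of interpretation. The comparison between arms at Visit 2 can combine profiles from during and after co-administration, and a finding of no difference could not be assigned clearly to either state. Whether this would change any pharmacokinetic estimate, and by how much, cannot be derived from the documents. The matter should be corrected because it touches the primary outcome and costs little; it does not by itself invalidate the study.

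**What to change.** 1. Reconcile sections 2.4, 4.3.2 and 4.3.3 so that the Visit 1 window, the course and the Visit 2 window agree with the stated interval from the last dose. State the day of the first dose and put a number on the interval. No particular timing is proposed here; that choice is for the investigators.
2. Record the date and time of the last clomiphene or letrozole dose.
3. Report the interval from last dose to the Visit 2 profile for each combination arm.
4. As exploratory description only, show Visit 2 pharmacokinetic results for profiles taken on or before the last-dose day separately from later ones.

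I would not add the interval as a model covariate. It is undefined in the EGCG-alone arm, it is fixed by the cycle days of the two visits and the first-dose day and so cannot be separated from cycle day, and there are only 36 / 3 = 12 women per arm. For the same reason of size, the split in item 4 may rest on very few women and should not be tested.

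The cost is protocol wording, one data field and slightly tighter visit booking.
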